### Table 9 specification

Repeat with ITT population and PP population separately as Table 9A-1 and Table 9A-2 as well as Table 9B-1 and Table 9B-2, respectively.

Table 10. Summary Statistics for Eosinophilic Esophagitis Symptom and Global Assessment Scores (Secondary Efficacy Endpoints)

	All	Viaskin® milk	Placebo	
Eosinophilic esophagitis symptom score				
Baseline				
0 (None)				
1 (Mild)				
2 (Moderate)				
3 (Severe)				
4 (Very severe)				
Visit 10				
0 (None)				
1 (Mild)				
2 (Moderate)				
3 (Severe)				
4 (Very severe)				
Visit 16				
0 (None)				
1 (Mild)				
2 (Moderate)				
3 (Severe)				
4 (Very severe)				
Change from baseline to visit 10				
-4 (Very severe to None)				
-3				
-2				
-1				
0 (No change)				
1				
2				
3				
4 (None to Very severe)				
Change from baseline to visit 16				
-4 (Very severe to None)				
-3				
-2				
-1				

Table 10. Summary Statistics for Eosinophilic Esophagitis Symptom and Global Assessment Scores (Secondary Efficacy Endpoints)

	All	Viaskin® milk	Placebo	
0 (No change)				
1				
2				
3				
4 (None to Very severe)				

Values will be expressed as frequency counts (percentages).

**Table 10 specifications**

Repeat with each individual eosinophilic esophagitis symptom scores (Abdominal/Chest pain, Vomiting/Regurgitation, and Dysphagia) as well as the investigator's global assessment scores on ITT population and PP population separately as Table 10-1A, Table 10-1B, Table 10-2A, Table 10-2B, Table 10-3A, Table 10-3B, Table 10-4A, and Table 10-4B, respectively.

Table 11. Summary Statistics for The Total Eosinophilic Esophagitis Symptom Score (Secondary Efficacy Endpoint)

	All	Viaskin® milk	Placebo	
Total eosinophilic esophagitis symptom score #				
Baseline				
Visit 10				
Visit 16				
Change from baseline to visit 10				
Change from baseline to visit 16				
Improvement in eosinophilic esophagitis total symptom score at visit 10 *				
Yes (Responders), n (%)				
No (Non-responders), n (%)				
Improvement in eosinophilic esophagitis total symptom score at visit 10 **				
Poor improvement (<30%), n (%)				
Good improvement (30-70%), n (%)				
Excellent improvement (>70%), n (%)				
Improvement in eosinophilic esophagitis total symptom score at visit 16 *				
Yes (Responders), n (%)				
No (Non-responders), n (%)				
Improvement in eosinophilic esophagitis total symptom score at visit 16 **				
Poor improvement (<30%), n (%)				

Table 11. Summary Statistics for The Total Eosinophilic Esophagitis Symptom Score (Secondary Efficacy Endpoint)

	All	Viaskin® milk	Placebo	
Good improvement (30-70%), n (%)				
Excellent improvement (>70%), n (%)				

# Values will be expressed as n, n missing, mean  $\pm$  SD, median (IQR), and range. Hodges-Lehmann median differences between two treatment groups will be reported.

\* Improvement in total eosinophilic esophagitis symptom scores is defined as a decrease in total symptom scores of two or more from baseline to end of the double-blind treatment (visit 10) and from baseline to end of the open-label treatment (visit 16). If change in total symptom score (Visit 10 – baseline or Visit 16 - baseline) is 2 or greater than 2, subject is responder; if not, subject is non-responder. Values will be expressed as frequency counts (percentages).

\*\* Improvement will be reported as Poor, Good, and Excellent as FDA requested.

Relative risk with 95% CI of the improvement between two treatment groups will be presented.

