11.12 Eosinophilic Esophagitis Symptom Score

Symptoms of Eosinophilic Esophagitis range from abdominal pain, gastroesophageal reflux, vomiting, and difficult swallowing. The symptoms will range from none to very severe as in Spergel⁵⁴. The symptoms will be in 3 categories and individual symptoms and total symptoms scores will be collected on a range of 0-4 (0-none, 1-mild, 2-moderate, 3-severe and 4-very severe).

Table 4: Eosinophilic Esophagitis Score

Symptoms	Score
Abdominal/Chest Pain	0-4
Vomiting/Regurgitation	0-4
Dysphagia	0-4
Total Score	0-12

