13.6.4.2 Secondary Efficacy Variables

The following secondary efficacy endpoints will be assessed:

Esophageal Eosinophil Count

The mean Esophageal Eosinophil Count of all specimens obtained at the end of treatment as well as the change from baseline will be summarized by treatment group.

The null hypothesis that the mean Esophageal Eosinophil Count eliciting doses at the end of treatment are the same in each treatment group will be analyzed using ANCOVA model with treatment group, baseline patient's mean esophageal eosinophil count, and age group (4-11 years old versus 12-17 years old) as covariates. This null hypothesis will be tested against the alternative hypothesis that the results are different in each treatment group at the 0.05 significance level.

Esophageal Endoscopy Score

The total score for each subject will be calculated (for endoscopy) and summary statistics will be presented for each treatment group at baseline and the end of study. This will be based on each symptom being graded for severity as 0, 1, 2 or 3 (respectively none, mild, moderate and severe). The total scores at the end of treatment between two treatment groups will be examined using ANCOVA model with treatment group, baseline patient's total score, and age group (4-11 years old versus 12-17 years old) as covariates. The change from baseline to end of treatment will also be presented. The change in Esophageal endoscopy scores between two treatment groups will be examined using a two sample Student's t-test or Mann-Whitney test.

Eosinophilic Esophagitis Symptom Score

Improvement in symptom scores will be defined as a decrease in total symptom scores of two or more from baseline to end of treatment. Subjects will be categorized based on whether they improved their symptoms. Subjects who improved their symptom scores were considered as responders and patients who did not improve their symptom scores were considered as non-responders. The percentage of responders between the active treatment group and placebo group will be compared using Fisher's exact test. In addition, all of the summaries of severity of symptoms above will be repeated, split by responder/non-responder groups.

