#### **2.2.4 Secondary efficacy endpoints**

The secondary efficacy endpoint measures are:

- a. The EoE symptom score and global assessment score at the end of each treatment period at 11 and 22 months (improvement in EoE symptom score will be defined as a decrease in total symptom score of two or more from baseline to the end of each treatment period at 11 and 22 months) as well as the change in EoE symptom score from baseline to the end of each treatment period at 11 and 22 months (e.g., the change in EoE symptom score at 11 month = the EoE symptom score at 11 month – (minus) the EoE symptom score at baseline, the change score is the difference) and the EoE frequency and severity symptom scores measured by Pediatric Eosinophilic Esophagitis Symptoms Score (PEESS) at the end of each treatment period at 11 and 22 months as well as the changes in these symptom scores from baseline to the end of each treatment period at 11 and 22 months.
- b. Mean esophageal eosinophil count which is the average of all of the samples obtained on biopsy at the end of each treatment period at 11 and 22 months.
- c. The changes in mean and maximum esophageal eosinophil count from baseline to the end of each treatment period at 11 and 22 months.
- d. The percentages of subjects with  $\leq 1$  eosinophil/HPF (excellent response), subjects with 2-14 eosinophils/HPF (good response), and subjects with  $\geq 15$

eosinophils/HPF (poor response) at the end of each treatment period at 11 and 22 months.

- e. Esophageal endoscopy score at the end of each treatment period at 11 and 22 months and the change in the esophageal endoscopy score from baseline to the end of each treatment period at 11 and 22 months.
- f. Changes in the eosinophilic esophagitis quality of life score from baseline to the end of each treatment period at 11 and 22 months.
- g. Changes in the composite score from baseline to the end of each treatment period at 11 and 22 months.
- h. Time to development symptoms after milk reintroduction at month 9 and 20.
- i. Changes in exploratory biologic markers, including T-regulatory cells, TSLP, and CBC with differential and milk-specific Immunoglobulin level and epigenetic changes.

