#### **4.4.2.2 Eosinophilic esophagitis symptom and global assessment scores**

Summary statistics for individual eosinophilic esophagitis symptom score (Abdominal/Chest pain, Vomiting/Regurgitation, and Dysphagia) as well as investigator's eosinophilic esophagitis global assessment score at baseline, end of the double-blind treatment, and end of the open-label treatment as well as changes from baseline to end of the double-blind treatment and to end of the open-label treatment will be presented by treatment groups and overall (*Table 10*). The total EoE symptom score for each subject will be calculated and summary statistics at baseline, end of the double-blind treatment, and end of the open-label treatment, as well as the changes from baseline to end of the double-blind treatment and to end of the open-label treatment will be presented by treatment groups and overall. Improvement in symptom scores will be defined as a decrease in total eosinophilic esophagitis symptom score of two or more from baseline to end of the double-blind treatment and to end of the open-label treatment. Subjects will be categorized based on whether they improved their symptoms in two different ways. First, subjects who improved their symptom scores are considered as responders and subjects who did not improve their symptom scores are considered as non-responders. Second, subjects who improved their symptom scores will be categorized as poor improvement (<30%), good improvement (30-70%), and excellent improvement (>70%). RR or OR along with 95%

CI for the percentage of responders between two treatment groups will be presented. (*Table 11*).

In addition, frequency and severity EoE symptom scores measured by Pediatric Eosinophilic Esophagitis Symptoms Score (PEESS) will be examined. Summary statistics for the frequency and severity EoE symptom scores at baseline, end of the double-blind treatment, and end of the open-label treatment will be reported for each treatment group and overall. The changes in frequency and severity EoE symptom scores from baseline to end of the double-blind treatment and to end of the open-label treatment will be reported and Hodges-Lehmann estimates with 95% CIs for differences of medians of these changes between two treatment groups will be reported (*Table 12*).

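### The responder rule in the SAP's Table 11 footnote has the wrong sign: it counts a worsening of two or more points as a response

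*SAP*

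**What the plan says.** Protocol 11.12 grades each of three symptoms as "0-none, 1-mild, 2-moderate, 3-severe and 4-very severe" and adds them to a total of 0 to 12, so a higher total means worse symptoms.

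The direction of a response is stated in words in four places:

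- Protocol 13.6.4.2: "a decrease in total symptom scores of two or more from baseline to end of treatment".
- SAP 2.2.4(a): "improvement in EoE symptom score will be defined as a decrease in total symptom score of two or more from baseline".
- SAP 4.4.2.2: "Improvement in symptom scores will be defined as a decrease in total eosinophilic esophagitis symptom score of two or more from baseline". The same section makes the children who improved the responders.
- SAP 5.1, Table 11 footnote, first sentence: "Improvement in total eosinophilic esophagitis symptom scores is defined as a decrease in total symptom scores of two or more from baseline".

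The second sentence of that footnote then turns the definition into a rule: "If change in total symptom score (Visit 10 – baseline or Visit 16 - baseline) is 2 or greater than 2, subject is responder". Everyone else is a non-responder.

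**The concern.** The footnote writes out the order of subtraction as follow-up minus baseline and sets the threshold at +2. On a scale where higher is worse, that selects children whose symptoms rose. Two adjacent sentences of one footnote therefore give responder groups that cannot overlap.

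The flag feeds the responder rows and the relative risk in Table 11 at Visits 10 and 16, repeated for the ITT population (Table 11A) and the per-protocol population (Table 11B). SAP 4.4.2.2 also applies the poor, good and excellent bands to the children who improved. If that group were picked with the same flag, those rows would be wrong too: every child selected would have got worse, so none could reach the 30% improvement needed for a good response.

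A reversed flag might not show itself through empty cells. SAP 4.4.1 dates baseline to Day 1 for the primary endpoint, when children are on a milk-free diet, and Visit 10 follows milk reintroduction. Protocol 10.3 expects that placebo subjects and treatment failures may have flares. If the symptom baseline is also Day 1 (the SAP does not date it separately, so this is an assumption), rises of two or more are plausible, and the literal rule would report them as responses.

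**Working it through.** **Inputs**

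- Total score: whole numbers 0 to 12 (Protocol 11.12).
- Definition D: baseline − follow-up ≥ 2 (Protocol 13.6.4.2; SAP 2.2.4(a) and 4.4.2.2; first sentence of the Table 11 footnote).
- Footnote rule F: follow-up − baseline ≥ 2 (second sentence of the same footnote).

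**Step 1: is the sign convention in doubt?** No. SAP 2.2.4(a) gives the change at 11 months as "the EoE symptom score at 11 month – (minus) the EoE symptom score at baseline". The Table 10 shell labels a change of −4 as the move from the worst grade to no symptoms. The footnote itself puts the visit first and baseline second. Negative means better throughout.

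**Step 2: count the score pairs.** There are 13 × 13 = 169 pairs of baseline and follow-up scores. A fall of exactly k points can occur in 13 − k ways.

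- Fall of 2 or more: 11 + 10 + … + 1 = 66.
- Rise of 2 or more: 66, by symmetry.
- Change of −1, 0 or +1: 169 − 66 − 66 = 37.

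| Pairs | Number | Under D | Under F |
|---|---|---|---|
| Fall of 2 or more | 66 | responder | non-responder |
| Change of at most 1 | 37 | non-responder | non-responder |
| Rise of 2 or more | 66 | non-responder | responder |

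The rules share no responder pair. They agree on 37 pairs and disagree on 66 + 66 = 132. For example, 6 → 2 (change −4) is a response under D but not under F; 2 → 6 (change +4) is the reverse.

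**Step 3: could another reading rescue the sentence?**

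- *Absolute change of 2 or more:* 132 pairs become responders, and the 66 worsening pairs among them are still misclassified.
- *A minus sign lost in the text (−2 or greater):* falls of 3 or more number 10 + 9 + … + 1 = 55, so 169 − 55 = 114 pairs would be responders. Only the 11 with a fall of exactly 2 meet D. Misclassified: (114 − 11) + 55 = 158.

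Neither reading reproduces the definition.

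**Step 4: test the correction.** Follow-up − baseline ≤ −2 disagrees with D on 0 of 169 pairs.

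**Step 5: weight of one child.** With 16 active and 6 placebo subjects (Protocol 13.2; SAP 2.4.2), one miscoded child moves the responder rate by 100/16 = 6.25 or 100/6 = 16.7 percentage points. SAP 3.2 gives 15 and 5 instead, which makes it 100/15 = 6.7 or 100/5 = 20 points.

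**The case against.** The intent is not in doubt. Four statements say decrease, one of them in the same footnote, and the Table 11 row itself is headed as improvement. The author probably meant a decrease whose size is 2 or greater. SAP 2.2.4(a) also supplies both the threshold and the order of subtraction, so the correct rule can be put together without the footnote. A careful programmer would do that, and because Table 11 prints the change scores beside the responder counts, a reversed flag might well be noticed. The endpoint is one of many secondary endpoints in a small pilot, and 132 of 169 gives every score pair equal weight, so it says nothing about how many children would be affected.

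Most of this stands, and it limits the harm: this is very probably a drafting slip, and the damage depends on how the table is coded. It does not make the sentence right. The footnote is the one place where threshold and subtraction appear together as an if-then rule, and it sits in the table shell that a programmer would use. A reader who follows it to the letter reverses the endpoint.

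**Conclusion.** The concern holds. The second sentence of the Table 11 footnote contradicts the definition of improvement used everywhere else in the protocol and SAP. Coded literally, it would classify every child who improves by two or more points as a non-responder and every child who worsens by two or more as a responder; only children who change by at most one point would be coded correctly.

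The conclusion rests on the direction of the scale and the stated order of subtraction, both explicit in the documents. It assumes no score distribution and makes no claim about how the table was in fact programmed. The effect is confined to the symptom responder endpoint at Visits 10 and 16, its relative risk, and any summary that reuses the flag. The primary ANCOVA on eosinophil count and the sample size are unaffected. It should be corrected before Table 11 is programmed.

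**What to change.** Replace the second sentence of the footnote with a rule such as: *Change is the Visit 10 (or Visit 16) total minus the baseline total; a subject whose change is −2 or lower is a responder, and every other subject is a non-responder.* This matches the definition on all 169 score pairs.

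The cost is a one-sentence correction to a table shell, with no new data and no change to the design. If Table 11 has already been programmed, check the sign in the code and rerun Tables 11A and 11B, along with any summary split by responder status.

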### Table 11 specification

Repeat with ITT population and PP population separately as Table 11A and Table 11B, respectively.

Table 12. Summary Statistics for Pediatric Eosinophilic Esophagitis Symptom Scores (PEESS) (Secondary Efficacy Endpoint)

	All	Viaskin® milk	Placebo	Median Difference (95% CI) #
Frequency Symptom Score				
Baseline				
Visit 10				
Visit 16				
Change from baseline to visit 10				
Change from baseline to visit 16				
Severity Symptom Score				
Baseline				
Visit 10				
Visit 16				
Change from baseline to visit 10				
Change from baseline to visit 16				
Frequency and Severity Symptom Score (Total score)				
Baseline				
Visit 10				
Visit 16				
Change from baseline to visit 10				
Change from baseline to visit 16				

Values will be expressed as n, n missing, mean  $\pm$  SD, median (IQR), and range.

# Hodges-Lehmann estimate with 95% CI for median differences between two treatment groups will be reported.

### Table 12 specifications

Repeat with ITT population and PP population separately as Table 12A and Table 12B, respectively.

Table 13A. Summary Statistics for Response rate at the End of the Double-blind Treatment (Secondary Efficacy Endpoint)

	All	Viaskin® milk	Placebo	Relative Risk (95% CI)
Response rate, n (%)				
Excellent ( $\leq 1$ eosinophils/HPF)				
Good (2-14 eosinophils/HPF)				
Poor ( $\geq 15$ eosinophils/HPF)				
Values will be expressed as frequency counts (percentages).				

Table 13B. Summary Statistics for Response rate at the End of the Open-label Treatment (Secondary Efficacy Endpoint)

	All	Viaskin® milk	Placebo	Relative Risk (95% CI)
Response rate, n (%)				
Excellent ( $\leq 1$ eosinophils/HPF)				
Good (2-14 eosinophils/HPF)				
Poor ( $\geq 15$ eosinophils/HPF)				
Values will be expressed as frequency counts (percentages).				

### Table 13 specification

Repeat on ITT population and PP population separately as Table 13A-1 and Table 13A-2 as well as Table 13B-1 and Table 13B-2, respectively.

Table 14. Summary Statistics for Eosinophilic Esophagitis Quality of Life Score (Secondary Efficacy Endpoint)

	All	Viaskin® milk	Placebo	Median Difference (95% CI) #
Quality of life score				
Baseline				
Visit 10				
Visit 16				
Change from baseline to visit 10				xx (xx, xx)
Change from baseline to visit 16				xx (xx, xx)

Values will be expressed as n, n missing, mean  $\pm$  SD, median (IQR), and range..  
 # Hodges-Lehmann estimate with 95% CI for median differences between two treatment groups will be reported.

**Table 14 specifications**

Repeat with ITT population and PP population separately as Table 14A and Table 14B, respectively.

Table 15. Summary Statistics for Composite score (Secondary Efficacy Endpoint)

	All	Viaskin® milk	Placebo	Median Difference (95% CI) #
Quality of life score				
Baseline				
Visit 10				
Visit 16				
Change from baseline to visit 10				xx (xx, xx)
Change from baseline to visit 16				xx (xx, xx)

Values will be expressed as n, n missing, mean  $\pm$  SD, median (IQR), and range.

# Hodges-Lehmann estimate with 95% CI for median differences between two treatment groups will be reported.

Composite score = Maximum Eosinophils per HPF + 10\*EREFS + 2\*PEESS +5\* (Investigator assessment of EoE symptom activity)

**Table 15 specifications**

Repeat with ITT population and PP population separately as Table 15A and Table 15B, respectively.

Table 16A. Detailed Listing for All Adverse Events by MedDRA System Organ Class

Adverse events were classified into SOC and PT using Version XX.0 of MedDRA.

The following coding will be used:

Severity: 1=Mild, 2=Moderate, 3=Severe, 4=Life-threatening, and 5=Death.

Grade: 1, 2, 3, and 4.

Causality: 1=Unlikely related, 2=Possibly related, and 3=Probably related.

Action taken: 0=None, 1=Prescribed medication, 2=Non-medication treatment, 3=Hospitalization or prolongation, 4=Discontinued treatment.

Outcome: 1=Ongoing (no change), 2= Recovering/resolving (improving), 3=Worsened, 4=Recovered/resolved with no sequelae, 5=Recovered/resolved with sequelae (chronic stable) 6=Death.

Table 16B. Detailed Listing for All Adverse Events by MedDRA Preferred Term

Adverse events were classified into SOC and PT using Version XX.0 of MedDRA.

The following coding will be used:

Severity: 1=Mild, 2=Moderate, 3=Severe, 4=Life-threatening, and 5=Death.

Grade: 1, 2, 3, and 4.

Causality: 1=Unlikely related, 2=Possibly related, and 3=Probably related.

Action taken: 0=None, 1=Prescribed medication, 2=Non-medication treatment, 3=Hospitalization or prolongation, 4=Discontinued treatment.

Outcome: 1=Ongoing (no change), 2= Recovering/resolving (improving), 3=Worsened, 4=Recovered/resolved with no sequelae, 5=Recovered/resolved with sequelae (chronic stable) 6=Death.

Table 17A. Adverse Events by System Organ Class (Number of subjects)

Adverse events were classified into SOC and PT using Version XX.0 of MedDRA.

Table 17B. Adverse Events by System Organ Class (Number of adverse events)

Adverse events were classified into SOC and PT using Version XX.0 of MedDRA.

Table 18. Summary of Adverse Events by Treatment Group

	All	Viaskin® milk	Placebo
Number of subjects (%) with AEs			
Number of AEs			
Number of AEs per subject			
0			
1			
2 +			
Number of systemic allergic symptoms			
Potentially drug-related			
Yes			
No			
Severity of AEs			
Mild			
Moderate			
Severe			
Life-threatening			
Death			
Serious AEs (SAEs)			
Yes			
No			
Number of potentially drug-related SAEs			
AE leading to discontinuation			
Yes			
No			
AE leading to death			
Yes			
No			
Ongoing			
Yes			
No			
Outcome			
Unchanged			
Worsened			
Recovered/resolved with no sequelae			
Recovered/resolved with sequelae			
Death			

Table 19A. Treatment-Emergent AEs (TEAEs)\* by Treatment Groups  
(Number of subjects (%))

	All	Viaskin® milk	Placebo
TEAEs			
Potentially drug-related TEAE			
Severity of TEAE			
Mild			
Moderate			
Severe			
Life-threatening			
Death			
Serious TEAE			
TEAE leading to discontinuation			
TEAE leading to death			
Number of TEAEs			
0			
1			
2			
3 +			
Ongoing			
Yes			
No			
Outcome			
Unchanged			
Worsened			
Recovered/resolved with no sequelae			
Recovered/resolved with sequelae			
Death			

\* Treatment-emergent AE is defined as any AE, regardless of relationship to study drug, which occur during AE collection period of study drug or an event already present that worsens in either intensity or relationship to study drug following exposure to Viaskin®.

Table 19B. Treatment-Emergent AEs (TEAEs)\* by Treatment Groups  
(Number of TEAE)

	All	Viaskin® milk	Placebo
Number of TEAEs			
Number of potentially drug-related TEAE			
Number of severity of TEAE			
Mild			
Moderate			
Severe			
Life-threatening			
Death			
Number of serious TEAE			
Number of TEAE leading to discontinuation			
Number of TEAE leading to death			
Number of TEAEs per subject			
0			
1			
2			
3 +			
Number of local TEAE			
Number of severity of local TEAE			
Mild			
Moderate			
Severe			
Life-threatening			
Death			
Outcome			
Unchanged			
Worsened			
Recovered/resolved with no sequelae			
Recovered/resolved with sequelae			
Death			

\* Treatment-emergent AE is defined as any AE, regardless of relationship to study drug, which occur during AE collection period of study drug or any event already present that worsens in either intensity or relationship to study drug following exposure to Viaskin®.

Table 20. Summary Statistics of Local Skin Reactions (Adverse Events)

	All	Viaskin® milk	Placebo	
Number of patients with reactions				
0				
1				
2				
3				
4				

Values will be expressed as frequency counts (percentages) unless indicated.

Table 21. Summary of Laboratory Abnormalities based on CTC Grade by Visit and Treatment Groups

	Viaskin®Milk				Placebo				
	Visit 1	Visit 8	Visit 10	Visit 16	Visit 1	Visit 8	Visit 10	Visit 16	
Hematology									
RBC Count									
WBC Count									
Hemoglobin									
Hematocrit									
Platelet Count									
Segmented Neutrophils									
Lymphocytes									
Monocytes									
Eosinophils									
Basophils									
Chemistry									
Total Protein									
Blood Urea Nitrogen									
Creatinine									
ALP									
ALT									
AST									
Total Bilirubin									

Values (abnormalities) will be expressed as frequency counts (percentages). Number of subject evaluated at each visit will be reported.

Treatment groups will be compared using Fisher's exact test.

ALP, Alkaline phosphatase; ALT, Alanine aminotransferase; AST, Aspartate aminotransferase.

Table 22. Summary of Clinically Relevant Abnormalities in Vital Signs by Visit and Treatment Groups

	Viaskin® Milk				Placebo			
	Temperature	Pulse	SBP	DBP	Temperature	Pulse	SBP	DBP
Visit 1								
Abnormal, n (%)								
Number of subjects evaluated								
Visit 2								
Abnormal, n (%)								
Number of subjects evaluated								
Visit 3								
Abnormal, n (%)								
Number of subjects evaluated								
Visit 4								
Abnormal, n (%)								
Number of subjects evaluated								
Visit 5								
Abnormal, n (%)								
Number of subjects evaluated								
Visit 6								
Abnormal, n (%)								
Number of subjects evaluated								
Visit 7								
Abnormal, n (%)								
Number of subjects evaluated								

Table 22. Summary of Clinically Relevant Abnormalities in Vital Signs by Visit and Treatment Groups

	Viaskin® Milk				Placebo			
	Temperature	Pulse	SBP	DBP	Temperature	Pulse	SBP	DBP
Visit 8								
Abnormal, n (%)								
Number of subjects evaluated								
Visit 9								
Abnormal, n (%)								
Number of subjects evaluated								
Visit 10								
Abnormal, n (%)								
Number of subjects evaluated								
Visit 11								
Abnormal, n (%)								
Number of subjects evaluated								
Visit 12								
Abnormal, n (%)								
Number of subjects evaluated								
Visit 13								
Abnormal, n (%)								
Number of subjects evaluated								
Visit 14								
Abnormal, n (%)								
Number of subjects evaluated								

Table 22. Summary of Clinically Relevant Abnormalities in Vital Signs by Visit and Treatment Groups

	Viaskin® Milk				Placebo			
	Temperature	Pulse	SBP	DBP	Temperature	Pulse	SBP	DBP
Visit 15								
Abnormal, n (%)								
Number of subjects evaluated								
Visit 16								
Abnormal, n (%)								
Number of subjects evaluated								
Visit 17								
Abnormal, n (%)								
Number of subjects evaluated								

SBP, Systolic Blood Pressure; DBP, Diastolic Blood Pressure.

Criteria for abnormalities:

Temperature: < 35 °C and a decrease from pre-dosing of at least 1 °C or >38.5 °C and an increase from pre-dosing of at least 1 °C.

Pulse: > 120 beats/minute or an increase from pre-dosing of > 20 beats/minute, or < 50 beats/minute or a decrease from pre-dosing of > 20 beats/minute.

SBP: > 140 mmHg or an increase from pre-dosing of > 40 mmHg, or < 90 mmHg or a decrease from pre-dosing of > 30 mmHg.

DBP: > 90 mmHg or an increase from pre-dosing of > 30 mmHg, or < 50 mmHg or a decrease from pre-dosing of > 20 mmHg.

